**** The maximum daily dose of Loperamide is 16 mg**

Version 1,
Dec, 12, 2017

Appendix 4 RASH MANAGEMENT RECOMMENDATIONS

RECOMMENDATIONS FOR ACNEIFORM RASH MANAGEMENT

Given the presence of wild type EGFR receptors in the skin, rash is a common, expected toxicity of tyrosine kinase inhibitor (TKI) compounds. For rash management, at the treating Investigator’s discretion, the following interventions are strongly recommended.

Early and regular contact with the PI or dermatologist should be arranged for and provided prior to initiating dosing. At Baseline, an education session should be provided to the patient to inform them of likely skin events while on study and directions given on how to contact the appropriate member of the health care team. Visits on **Days 8 and 15** should include a focus on skin and mucosal assessment. Per protocol, visits or telephone contact should be made with the patient every week during **Cycles 1 and 2** and then every 2 weeks while being treated with study drug.

Supportive medications, including early steroid use, should be considered even in the presence of low-grade “on-target” toxicity (eg, rash).

Preliminary information from **Cohort 1** suggest that dose interruptions should be minimized in order to reduce the risk of progression.

CTCAE Severity Grading of Rash

Skin and subcutaneous tissue disorders	GRADE				
	1	2	3	4	5
Rash Acneiform	Papules and/or pustules covering <10% BSA, which may or may not be associated with symptoms of pruritus or tenderness	Papules and/or pustules covering 10 - 30% BSA, which may or may not be associated with symptoms of pruritus or tenderness; associated with psychosocial impact; limiting instrumental ADL	Papules and/or pustules covering >30% BSA, which may or may not be associated with symptoms of pruritus or tenderness; limiting selfcare ADL; associated with local superinfection with oral antibiotics indicated	Papules and/or pustules covering any % BSA, which may or may not be associated with symptoms of pruritus or tenderness and are associated with extensive superinfection with IV antibiotics indicated; life-threatening consequences	Death

Rash Definition: A disorder characterized by an eruption of papules and pustules, typically appearing in face, scalp, upper chest and back.

Abbreviations: ADL = activities of daily living; BSA = body surface area;

RECOMMENDATIONS FOR RASH MANAGEMENT

RASH SEVERITY	INTERVENTION

Start Prophylaxis for Rash (CTCAE Grade 0)
 
Initiation of Poziotinib Treatment
	
 • Baseline Visit: Expected skin events and management education session. • On initiation of Poziotinib therapy consider starting prophylactic treatment with doxycycline or minocycline for 4 weeks, if there are no contraindications.

Mild Rash (CTCAE Grade 1)
 
Generally localized Minimally symptomatic No impact on ADL No sign of infection
	
 • For Face/Body Folds or Body: Initiate low/moderate dose oral steroids (e.g., dexamethasone or prednisone). Start topical therapy (e.g., hydrocortisone 2.5% cream or ointment [Class VII topical steroid]) BID on the affected areas. • Consult dermatologist. • Continue poziotinib at the current dose level

Moderate Rash (CTCAE Grade 2)
 
Generalized Mild symptoms (e.g., pruritus, tenderness) Minimal impact on ADL No sign of superinfection
	
 • For Face/Body Folds: Initiate/continue with high-dose oral steroids (e.g., dexamethasone or prednisone) for 5-7 days and reassess. Start/change hydrocortisone to triamcinolone 0.1% cream or ointment (Class IV topical steroid) BID and consider adding topical clindamycin cream 1% BID on the affected skin area. • For Body: Initiate/continue with high dose oral steroids (e.g., dexamethasone or prednisone) for 5-7 days and reassess. Consider start/change triamcinolone to clobetasol or betamethasone 0.05% cream or ointment (Class I topical steroid) BID and add topical clindamycin cream 1% BID on the affected skin area. • Consult dermatologist. • Continue poziotinib at the current dose level

Severe Rash (CTCAE Grade 3)
 
Generalized Severe symptoms (e.g., pruritus, tenderness) Potential for superinfection
	
 • Initiate/continue with high dose oral steroids (e.g., dexamethasone or prednisone) for 5-7 days. Continue until improvement/stabilization of rash to Grade ≤ 1. • Continue all Grade 2 skin management above. Consult dermatologist. • Discuss with Sponsor's Medical Monitor and consider brief poziotinib dose interruption/lower dose. • A dose "hold" of poziotinib should be for as short a time as possible (<5-14 days). Restart at the current poziotinib dose or next lower dose upon discussion with Sponsor's Medical Monitor.

Severe or Extensive Rash; Possibly Life-Threatening (CTCAE Grade 4)
 
Generalized severe or extensive symptoms; possibly life-threatening (e.g., pruritus, tenderness), associated with extensive superinfection
	
 • Consult Sponsor's Medical Monitor • If considered life-threatening, discontinue poziotinib immediately

Dexamethasone may affect the metabolism of poziotinib (metabolized by CYP3A4). Steroids that do not affect poziotinib metabolism (e.g., hydrocortisone, methylprednisolone) should be considered as substitute. Consult the Sponsor's Medical Monitor if needed.

Modified from: <http://www.aafp.org/afp/2009/0115/p135.pdf>

- Hirsh, V. Managing Treatment-Related Adverse Events Associated with EGFR Tyrosine Kinase Inhibitors in Advanced Non-Small-Cell Lung Cancer. Current Oncology.18.3.126-138.

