1.1.2.5.2 Overview of Safety

Overall, 1143 patients have received poziotinib in 21 clinical studies (12 sponsored by Hanmi, 8 Sponsored by Spectrum, and 1 by MD Anderson Cancer Center) at doses ranging from 0.5 mg to 32 mg QD on an intermittent dosing schedule or 10 mg to 24 mg QD on a continuous dosing schedule. Combined, more than 500 patients have been treated orally with 16 mg QD as their starting daily dose representing a large safety dataset for this rare mutation.

[figure not shown]
In **SPI-POZ-201**, a phase 2 study of patients with HER2-positive metastatic breast cancer, as of the cutoff date 12 Dec 2017, 32 (97.0%) patients in Cohort 1 have experienced treatment-emergent adverse events. The most common adverse event in Cohort 1 was diarrhea (87.9%), followed by rash (60.6%). In Cohort 1, 13 (39.4%) patients experienced serious adverse events.

In **SPI-POZ-202**, a phase 2 study of patients with locally advanced or metastatic non-small cell lung cancer with EGFR or HER2 exon 20 mutations, as of the cutoff date, 29 Jul 2018, 30 (96.8%) patients in Cohort 1 and 16 (84.2%) patients in Cohort 2 have experienced treatment-emergent adverse events. The most common TEAEs in Cohort 1 were also diarrhea (74.2%),

stomatitis (64.5%), and rash (48.4%). The most common TEAEs in Cohort 2 were diarrhea (73.7%), stomatitis (47.4%), and rash (52.6%). Diarrhea, stomatitis, and rash were also the most common treatment-related TEAEs in both cohorts.

In SPI-POZ-202, Cohort 5, poziotinib is being administered at varying doses (10 mg QD, 6 and 8 mg BID) to patients with NSCLC with EGFR and HER2 mutations. Patients treated with 8 mg BID have demonstrated improved tolerability and safety as compared to once daily dosing with 16 mg QD. As shown in **Figure 16**, patients treated with 8 mg BID had reduced treatment emergent \geq Grade 3 AEs and treatment-related AEs [Le et al, 2021]. Preliminary response data also showed improved anti-tumor activity with 8 mg BID dosing compared to 10, 12, 16 mg QD or 6 mg BID. Patients are continuing to be enrolled at the 8 mg BID starting dose.

Figure 16 Safety Comparison of 16 mg QD vs 8 mg BID

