 - Cohort 3: Patients that have solid tumors (except NSCLC, breast cancer, or colorectal cancer) with HER2 activating mutations (see [Table A](#)) (N=30)
 - Cohort 4: Patients that have GBM with EGFR activating mutations (see [Table A](#)) (N=30)
 - Cohort 5: Patients that have solid tumors (except NSCLC or GBM) with EGFR activating mutations (see [Table A](#)) (N=30)

Table A—List of Activating Mutations Eligible for Enrollment

Activating Mutations	
Cohorts 1-3: HER2 Activating Mutations (at least one of the following)	
Furin-Like/Extracellular	S310F/Y
Transmembrane	I655V, V659E, R678Q, V697L
Kinase Domain	Exon 20 insertion, T733I, L755X, I767M, D769X, V773M, V777X, L786V, V842I, T862I, L869R
Cohorts 4-5: EGFR Activating Mutations (at least one of the following)	
Extracellular & Transmembrane	EGFRvIII, R108K, R222C, A289T, P596L, G598V
Kinase Domain	Exon 20 insertion, E709X, E709_T710del insD, L718X, G719X, I740_K745dupIPVAIK, I740_K745dup, V742I, L747X, E746_A750del, A750P, S768I, S768I/V769L, S768I/V774M, L833V, V769M, V774M, R831C, R831H, L858R, L861Q, A864V

7. Patient has measurable disease, as per the Response Evaluation Criteria in Solid Tumors (RECIST, version 1.1) and/or RANO Criteria for **Cohort 4**. Target lesion(s) must be radiographically measurable. CNS metastatic lesions cannot be considered target lesions in **Cohorts 1-3** and in **Cohort 5**.
8. Brain metastases may be allowed if the patient's condition is stable. Stable condition is defined as having stable neurological symptoms, with no requirement for anti-seizure medications or >2 mg/day dexamethasone equivalent or increasing doses of systemic corticosteroids (except **Cohort 4** where anti-seizure medication [Keppra] and dexamethasone up to or equivalent to 4 mg daily is allowed), and no evidence of CNS disease progression documented for at least 4 weeks after CNS-directed treatment (eg. whole brain radiation), as ascertained by clinical examination and brain imaging (MRI or CT) during the screening period. Patients must complete CNS-directed treatment and return to stable condition prior to eligibility assessment for the study. For patients who have had radiation therapy, post-treatment MRI tests should show no increase in brain lesion size/volume and no new lesions compared to pre-treatment MRI (except **Cohort 4**) for at least 4 weeks. A new lesion is defined as lesion size greater than 5 mm and not previously present.

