5.4.9 Tumor Assessment

Tumor assessment for study patient's eligibility must be performed by Investigators using computed tomography (CT), positron emission tomography (PET)/CT, or magnetic resonance imaging (MRI) for non-brain organs and MRI for brain at **Screening** up to 30 days prior to **Cycle 1, Day 1**. Imaging studies performed prior to the signing of Informed Consent as part of the site's routine standard of practice are allowed at the discretion of the Sponsor as the Screening assessment. Brain MRI must be performed to assess the brain metastasis status at the screening per eligibility criteria. This information is to be discussed with the Sponsor's Medical Monitor before the patient is enrolled in the study. **Baseline** tumor assessment will be performed within 2 weeks prior to, or on **Cycle 1, Day 1**. Post-Baseline tumor assessments must be performed at **Cycle 2 Day 1**, at **Cycle 3 Day 1**, and every 8 weeks thereafter until patient discontinuation.

Each subsequent tumor assessment must use the same radiologic technique as in Baseline, either CT, PET/CT, or MRI. Tumor assessments will be made according to RECIST, version 1.1 [14] using appropriate radiologic imaging or other techniques. For radiographic assessment, CT, PET/CT, or MRI must be performed at every assessment.

In Cohort 4, tumor assessments will be made using appropriate radiologic imaging techniques as per RECIST 1.1 and/or the RANO criteria [15].

Measurable and non-measurable lesions should be documented appropriately.

Tumor assessment is based on the study investigator's assessment with local radiology review and report according to the RECIST 1.1 and/or RANO (for **Cohort 4**) criteria for response evaluation.

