5.4.11.2 Premedication and Supportive Treatment

Pre-medications, as per Institutional standard of care as determined by the Investigator, should be administered before poziotinib on **Day 1**. All supportive medications for potential diarrhea and rash management should be distributed to the patient on **Day 1** with instructions on their use.

Supportive medications, including early steroid use, should be considered even in the presence of low-grade "on-target" toxicity (eg, rash, diarrhea).

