8.1 Sample Size

The statistical analysis of each cohort will be performed separately. A total of 30 patients in each cohort will be enrolled using Simon's two-stage design. The optimal two-stage design to test the null hypothesis that $p \leq 0.050$ versus the alternative that $p \geq 0.250$ has an expected sample size of 16.76 and a probability of early termination of 0.630. If the drug is not effective, there is a 0.049 probability of concluding that it is (the target for this value was 0.050). If the drug is effective, there is a 0.098 probability of concluding that it is not (the target for this value was 0.100). For each cohort, 9 patients will be evaluated in the first stage; the cohort will be terminated if 0 respond. If the cohort goes on to the second stage, a total of 30 patients will be studied. If the total number responding is less than or equal to 3, the cohort is closed.

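### Cohort 4 (GBM) response can be scored on RECIST 1.1 alone with no stated steroid condition, while Appendix 4 recommends oral steroids from Grade 1 rash, so steroid-related shrinkage can enter the primary ORR

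*Combined protocol and SAP*

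**What the plan says.** **Response in Cohort 4.** Section 5.4.9: "In Cohort 4, tumor assessments will be made using appropriate radiologic imaging techniques as per RECIST 1.1 and/or the RANO criteria [15". Section 8.5 repeats the choice of criteria, bases the call on local review by the investigator, and counts only responses confirmed 4 weeks ± 3 days after the first CR or PR. Section 3.1 is softer and says that a confirmatory scan may be done. Neither 5.4.9 nor 8.5 mentions corticosteroid dose.

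**Steroids at entry.** Inclusion criterion 8 (Section 4.1) makes an exception for Cohort 4: "dexamethasone up to or equivalent to 4 mg daily is allowed". This is the only Cohort 4 steroid limit in the protocol's own text. The same criterion treats a need for increasing systemic steroids as incompatible with stable brain disease.

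**Steroids on study.** At Grade 1 rash, Appendix 4 recommends: "Initiate low/moderate dose oral steroids (e.g., dexamethasone or prednisone". No duration is given in that row. Grade 2 is a high-dose course of 5-7 days followed by reassessment. Grade 3 is a high-dose course continued until the rash improves or stabilizes to Grade 1 or less. Section 5.4.11.2 adds: "Supportive medications, including early steroid use, should be considered even in the presence of low-grade". None of these passages excepts Cohort 4. Appendix 4 is strongly recommended but at the investigator's discretion, and Section 5.4.11.2.3 allows standard of care.

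**Data.** Section 5.4.11 has all medications recorded on the CRF. Nothing links them to the response call.

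**The concern.** The drug's own toxicity management may feed a confounder of the primary endpoint in the one cohort whose target disease is in the brain. If corticosteroids reduce the measured lesion on brain MRI, a course begun for rash could produce an apparent PR without anti-tumor effect. That steroids do this in glioblastoma is general clinical knowledge and is not stated in the protocol. The protocol does treat steroid dose as relevant to brain-lesion stability at entry, and then drops it when response is scored.

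At stake are two decisions with low thresholds. One response among 9 patients opens stage 2, and 4 among 30 pass the final rule. The stage 1 decision is taken while the cohort is enrolling, whereas Section 8 promises the SAP only before database lock. A rule first written there could not undo an expansion already made.

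**Working it through.** **1. Does the timing allow it?**
- The baseline scan is within 2 weeks before, or on, Cycle 1 Day 1 (5.4.9), before any steroid for poziotinib rash.
- Appendix 4 directs skin assessment to the Day 8 and Day 15 visits.
- Post-baseline scans fall at Week 4 and Week 8.

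A steroid started for rash in Cycle 1 therefore falls between baseline and the first scan. A 5-7 day course would normally be over well before a confirming scan 4 weeks later. A Grade 1 course without an end date, or a Grade 3 course tied to improvement, could span both scans.

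**2. Reproduce the design (Section 8.1).** Inputs: null ORR 0.05, alternative 0.25, stop at 0/9, negative at 3/30 or fewer. Let X1 be responses in the first 9 patients and X2 responses in the next 21.
- P(stop early) = (1 − p)^9
- Expected N = 9 + 21 × [1 − P(stop early)]
- P(pass) = Σ over x1 ≥ 1 of P(X1 = x1) × P(X2 ≥ 4 − x1)

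At p = 0.05: P(stop early) = 0.95^9 = 0.630, expected N = 9 + 21 × 0.370 = 16.76, P(pass) = 0.0489. At p = 0.25: P(pass) = 0.9019, so the type II error is 0.0981. These match the protocol, which says "there is a 0.049 probability of concluding that it is" and "there is a 0.098 probability of concluding that it is not".

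**3. Effect of false responses.** Assume a true ORR of 5%, a share e of patients exposed to rash steroids, and a share q of exposed non-responders with a confirmed steroid-related PR. Then apparent ORR = 0.05 + 0.95 × e × q.

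| e | q | Apparent ORR | P(stage 2 opens) | P(pass 4/30) |
|---|---|---|---|---|
| any | 0 | 0.0500 | 0.370 | 0.049 |
| 0.25 | 0.05 | 0.0619 | 0.437 | 0.090 |
| 0.50 | 0.02 | 0.0595 | 0.424 | 0.081 |
| 0.50 | 0.05 | 0.0738 | 0.498 | 0.145 |
| 0.50 | 0.10 | 0.0975 | 0.603 | 0.278 |
| 0.50 | 0.20 | 0.1450 | 0.756 | 0.562 |

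The value e = 0.50 is loosely anchored. Section 1.1.2.5.2 gives any-grade rash of 48.4%, 52.6% and 60.6% in other tumor types, in data cut in 2017-2018. These are rash rates, not steroid uptake. No value of q is in the documents.

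**4. Cost of a strict exclusion rule.** At a true ORR of 25%, if every exposed responder were excluded and e = 0.50, the countable ORR is 0.25 × 0.50 = 0.125 and P(pass) = 0.447. If half of the exposed were excluded, it is 0.25 × 0.75 = 0.1875 and P(pass) = 0.752. The design value is 0.902.

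**The case against.** Four points count against a stronger form of this concern.

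- **RANO may already cover it.** A reader might infer that no steroid condition applies to Cohort 4 at all. The documents do not show that. RANO is brought in by citation and its content is not reproduced, so whether it conditions response on steroid dose cannot be checked here. The gap is shown for the protocol's own text and for the RECIST-only route, which is open because of the and/or. This stands and limits the claim.
- **Rash steroids are not mandated.** A reader might take Appendix 4 as starting steroids in every patient with rash. It is discretionary advice with standard of care as an alternative. This also stands, although a strong recommendation will still produce exposure, varying by site. Appendix 4's note on substitutes for dexamethasone does not remove the problem, because the substitutes it names are also corticosteroids.
- **Confirmation protects.** A false PR must persist at a second scan about 4 weeks later. That deals with short courses, but not with the open-ended Grade 1 row or prolonged Grade 3 use. Patients who enter already on dexamethasone may also have less added exposure.
- **The size is assumed.** Quoting only 28% and 56% would show the upper part of a range that also contains 8% and 14%, and Section 1.1.2.5.2 reports better tolerability at 8 mg BID than at 16 mg QD. This stands.

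One might add that later steroid tapering would shorten DoR and PFS. That is speculative, and both endpoints are descriptive, so it is not relied on.

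**Conclusion.** The concern holds in limited form. As written, a Cohort 4 response may be called on RECIST 1.1 alone, without regard to steroid dose at either scan, while the protocol recommends systemic steroids from Grade 1 rash with no Cohort 4 exception. Steroid-related shrinkage can therefore enter the primary ORR and the stage 1 count.

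The size cannot be derived from the documents. With half of patients exposed and 2% to 20% of exposed non-responders falsely scored as confirmed PR, the chance of passing an inactive drug runs from about 8% to 56%, against 4.9% by design. Even the low end exceeds the 5% target, because the thresholds are 1 of 9 and 4 of 30. These figures rest on the assumed exposure, the assumed false-PR rate and the steroid effect itself. They show how sensitive the rule is and do not predict the bias.

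**What to change.** 1. In Sections 5.4.9 and 8.5, and the matching synopsis text, replace the RECIST 1.1 and/or RANO choice for Cohort 4 with one governing criterion. RANO is already cited. A response could then not be called on RECIST alone.
2. Record the daily corticosteroid dose (dexamethasone-equivalent, any indication including rash) at baseline and at each Cohort 4 scan.
3. Prespecify, before the stage 1 decision, a steroid-restricted ORR for Cohort 4: a CR or PR counts as non-response if the steroid dose at the first or confirming scan is above the Cycle 1 Day 1 dose. Report it beside the primary ORR and at stage 1. This covers the question whatever RANO itself requires.
4. The sponsor should reconcile Appendix 4 with the Cohort 4 response definition. Nothing here changes rash care.

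The cost is a wording change, one CRF field and one extra table; concomitant medications are already collected. The steroid-restricted ORR may miss true responses: in the extreme case in the working, its chance of passing falls from 90% to about 45%. It should therefore sit beside the primary ORR and not act as a hard cap on best response.

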Appendix 5 PARONYCHIA MANAGEMENT RECOMMENDATIONS

RECOMMENDATIONS FOR PARONYCHIA MANAGEMENT

For paronychia management, at the treating investigator’s discretion, the following interventions may be used based on the severity of the paronychia.

PARONYCHIA SEVERITY	INTERVENTION

Mild Paronychia *(CTCAE Grade 1)
 
Nail fold edema or erythema; disruption of the cuticle
	
 • Dilute white vinegar/dilute bleach soaks • Avoid trauma, wet-work, friction • Betamethasone dipropionate 0.05% lotion or gel: Apply once or twice daily to the effected nail after the soak • Clindamycin gel or gentamicin solution: Apply once or twice daily after the soak • Continue Poziotinib at the same dose level • Consider a dermatology consult

Moderate Paronychia *(CTCAE Grade 2)
 
Local intervention indicated; oral intervention indicated (e.g., antibiotic, antifungal, antiviral); nail fold edema or erythema with pain; associated with discharge or nail plate separation; limiting instrumental ADL
	
 • If discharge from under or around the nail: Send wound discharge for culture • Betamethasone dipropionate 0.05% lotion or gel: Apply once or twice daily to the effected nail after the soak • Clindamycin gel/gentamicin solution: Apply once or twice daily after the soak • Key intervention: Consider consulting dermatology and chemical cautery with silver nitrate for periungual pyogenic granulomas • Consider partial nail avulsion if ingrown nail is visible. • Start antibiotics per wound culture or continue empiric Doxycycline 100 mg orally (or alternatively use Minocycline 100 mg orally) twice a day for 2-4 weeks or till resolution • Consider Poziotinib dose reduction after consultation with sponsor • Continue all CTCAE recommendations unless otherwise stated

Severe Paronychia *(CTCAE Grade 3)
	
 • Key intervention: Consider chemical cautery with silver nitrate for periungual pyogenic granulomas

Operative intervention indicated; IV antibiotics indicated; limiting self-care ADL	→	
 • Consider partial or total nail avulsion if ingrown nail is visible. • Oral or IV antibiotics as per wound culture sensitivity • Hold Poziotinib • Continue all CTCAE recommendations unless otherwise stated
--	---	---

